Sample Size: As this is a feasibility study, the primary concerns are whether or not this process could be incorporated into the normal anticoagulation clinic procedures and workflow. Results from this study can be utilized for calculating sample size and power statistical tests in future larger studies.

Analysis:

Accrual rate will be determined by average participants enrolled per week. Dropout rate will be determined by the number of participants lost to follow up out of the total number of participants

enrolled. Descriptive statistics (percentages, means, rates, and standard deviations) will be determined for all recorded baseline variables. Differences from baseline and at study completion will be compared utilizing McNemar Test for categorical data and paired t-test or Wilcoxon Signed-Rank Test for continuous and ordinal data (respectively). Thematic analysis will be utilized for to determine themes of satisfaction and/or concerns and barriers regarding the extended follow-up protocol from of the focus groups.

References

4. Guidelines on oral anticoagulation: third edition. *Br J Haematol*. May 1998;101(2):374-387.

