2. To assess the safety of extending the interval of INR follow-up in patients.

Hypothesis: We hypothesize that there will not be a difference between the bleeding and thromboembolic events from baseline (12 months prior to study enrollment) to events/year at 6, 12, and 24 months.

Hypothesis: We hypothesize that there will not be a difference in the patient's time in therapeutic range (TTR) from baseline (12 months prior to study enrollment) compared to the TTR at 12 and 24 months.

3. To examine patients' and providers' acceptance of the intervention (to extend the follow-up interval of INR monitoring).

Hypothesis: We hypothesize that both patients and providers will favorably view the intervention.

Background:

Anticoagulation treatment with vitamin K antagonists, such as warfarin, can be complicated by many variables, such as drug interactions, diet, health status, other medications, and adherence. Frequent INR monitoring is required to keep patients' INR values within their target therapeutic range to lower the risk of hemorrhagic or thrombotic adverse events. However, some patients remain on the same warfarin dose with INRs within their goal range for extended periods of time. Predictors of very stable INR control for patients on long-term anticoagulation with warfarin include age greater than 70 years, male gender, INR target less than 3.0, and absence of heart failure, diabetes, or other chronic diseases.^{1, 2}

The most recent American College of Chest Physicians 2012 guidelines recommend an INR testing frequency of up to 12 weeks over 4 weeks in patients on warfarin with consistently stable INRs (Grade 2B; weak recommendation, moderate-quality evidence).³ The guidelines define stable INRs as at least 3 months of INRs that are within therapeutic range, thus not requiring changes in warfarin dose. These guidelines are now more comparable to those from the United Kingdom, where the practice of a 12-week INR monitoring interval has been usual practice.⁴ Despite the guideline recommendations, many United States anticoagulation providers are hesitant to extend the duration of INR follow-up to 12 weeks, as historically, the recommended interval and standard clinical practice for INR follow-up was a maximum of 4-6 weeks.

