- Fatal or symptomatic bleed into a critical area or organ
- Bleeding leading to hospitalization
- Transfusion of 2 units or more packed red blood cells

Serious

- Bleeding leading to ED or UC visit or additional testing

After a major bleed, the participant will be removed from the extended follow-up interval and will not be eligible to qualify for the extended follow-up interval for 6 months after the event. After a serious bleed, the patient will be managed with usual care. If they did not have a permanent weekly dose change or if the temporary dose change was less than or equal to one month in duration, they must have 2 therapeutic INRs 4 weeks apart to begin the extended INR interval protocol.

If at any time a participant reports or clinic staff are alerted to a thromboembolic event, it will be documented in the EMR. The participant will be removed from the extended follow-up interval and not be eligible to qualify for the extended follow-up interval for 6 months after the event.

If at any time, anticoagulation clinic study staff do not feel it is appropriate to continue a participant with an extended follow-up interval, the participant can return to usual care. If at any time, the participant does not want to continue with an extended follow-up interval, they can return to usual care.

A participant will no longer be eligible for an extended INR interval if they meet any of the exclusion criteria at any time during the study, except for a bleeding or thromboembolic event. If a major bleeding or thromboembolic event occurs, they will be eligible to requalify after being on a stable warfarin dose for 6 months. A patient will also no longer be eligible for the extended INR interval if their INR goal changes and is no longer 2-3. A participant will be withdrawn from the study and no more data collected from the participant if they withdrawal their consent for the study or if death occurs.

A data monitoring committee will review the data collected, including bleeding and thromboembolic events for safety, protocol violations, and feasibility data at six months after the last patient is enrolled (at 3 months or when the 75th patient is enrolled), and then annually. If the data monitoring committee feels that the study is safe to continue, the study will continue until patients have been enrolled in the study for 2 years.

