The events rates for 2013 clinic data are listed below, including a 95%CI. Additionally, ranges for event rates over the past 4 years are included.

- Major bleed: 1.88% (95%CI 1.3-2.62%); range of 1.8-2%
- Serious bleed: 0.5% (95%CI 0.23-0.94%); range of 0-0.5%
- Thromboembolism: 0.22% (95%CI 0.06-0.6%); range of 0.2-0.44%

Stoppage rules for the study:

1. Stoppage rules for the study (based on event rates from the Schulman, et al. article) are included below. If the study is stopped early, all subjects will be scheduled for an INR within 6 weeks of their last INR, which is usual practice for the clinic.

Data from Schluman study				Madison VA	
Event	# from Schulman study	Rate per 1 year	95%CI of the 1 year rate from Schulman	Approx Count Based on 50 patients enrolled using upper end of 95% CI	Stoppage of Study
TE (includes TE-related death)	4	1.6%	0.4-4	2	3
Composite of TE, TIA, and major bleeding, TE-related death	12	4.8%	2.5-8.2	4.1	5

2. If an event occurs:
 - a. The PI or one of the Co-PIs will thoroughly evaluate the event to determine if it was related to study participation. . The following chart will be used to determine if the event was related to study participation.

Bleeding or TE event [‡]	On Extended Interval at Time of Event or within 6 Weeks of Event	INR Measure at visit following extended interval and/OR at Time of Event	Relationship to Hemostasis (as relates to INR direction/ magnitude)	Level of Attribution
Yes	Yes	Within target range	-	Possible
Yes	Yes	Outside target range	No relationship or uncertainty	Possible
Yes	Yes	Outside target range	Possible relationship	Probable
Yes	Yes	Outside target range	Definite relationship	Definite*

*Stopping rules apply to the events with a definite attribution. (Additional events may apply based on the discretion of the DMC and IRB.)

[‡] If the event was due to accident, injury, or other clear cause, attribution may not follow table.

- b. If a patient has a major bleeding or thromboembolic event, our protocol states that the patient will return to usual care and must be on the same dose for 6 months until they are able to requalify for the extended INR interval.

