Adverse events (AEs) collected for this study only include bleeding and thromboembolic events. Serious adverse events (SAEs) will be documented per VA and IRB definitions. AEs will be entered into OnCore after the retrospective review of the medical record at 6, 12, and 24 months after participant enrollment in the study. SAEs are entered into the SAE documentation area in OnCore as they occur, which may not align with the time period for the chart review. The SAEs that include bleeding or thromboembolism will be entered in real-time to the AE table in OnCore.

Measures: The outcomes of this study include feasibility, safety, and acceptability of extending the interval of INR follow-up to 12 weeks in stable warfarin patients. We propose to use the following measures:

1. Feasibility: We will examine the following:
 - a. Rates of participant accrual (patient interest in participating and reasons for not participating). Number of withdrawals and reasons for withdrawal from protocol or study.
 - b. Change in frequency of appointments from baseline
 - c. Frequency and type of protocol deviations from both participants and study staff
 - d. Frequency of time outside of extended INR interval protocol and why
 - e. Knowledge assessment of study staff regarding study protocol
2. Safety: We will examine the following:
 - a. Participant reported and EMR review of bleeding events. Study participant bleeding events for 12 months prior to enrollment and during the study will be compared to the clinic's bleeding event rate. The following definitions will be used to categorize bleeding:
 - i. Major
 1. Fatal or symptomatic bleed into a critical area or organ
 2. Bleeding leading to hospitalization
 3. Transfusion of 2 units or more PRBCs
 - ii. Serious
 1. Bleeding leading to ED or UC visit or additional testing
 - b. Participant reported and EMR review of thromboembolic events that are objectively verified. Study participant thromboembolic events for 12 months prior to study enrollment and during the study will be compared to the clinic's thromboembolic event rate.
 - c. Participant reported and EMR review of healthcare utilization: hospitalizations, ED visits, urgent office visits, telephone triage related to anticoagulation. Utilization for 12 months prior to study enrollment will be compared to utilization during study enrollment.
 - d. Baseline TTR (12 months prior and 6 months prior) for each patient and during study¹⁴
 - e. Number of extreme INRs (<1.5, ≥4.5)

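### Aim 2 predicts no change in events or TTR, but the Analysis section plans only difference tests, with no confidence interval for any change

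*Combined protocol and SAP*

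**What the plan says.** Specific Aims, Aim 2, states two hypotheses. For events, "there will not be a difference between the bleeding and thromboembolic events from baseline" (the 12 months before enrolment) to "events/year at 6, 12, and 24 months". For TTR, no difference is expected in the patient's "time in therapeutic range (TTR) from baseline (12 months prior to study enrollment) compared to the TTR at 12 and 24 months".

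The Analysis section gives the method for change from baseline: "Differences from baseline and at study completion will be compared utilizing McNemar Test for categorical data", with a paired t-test for continuous and a Wilcoxon signed-rank test for ordinal data. It names no confidence interval, margin, significance level or rule for concluding that there is no difference. Its descriptive statistics are confined to baseline variables. The only intervals in the document, beside the stoppage rules under Safety, belong to the clinic's 2013 rates and to the published trial used for those rules.

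Measures, items 2a and 2b, also compare participants' events with the clinic rate, without naming a method. Item 2c says "Utilization for 12 months prior to study enrollment will be compared to utilization during study enrollment". It gives no per-year scale, although "the study will continue until patients have been enrolled in the study for 2 years".

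**The concern.** A difference test can count against a hypothesis of no difference but cannot establish it. With few events, a non-significant result is likely whether or not risk has changed, and it is also the result that Aim 2 predicts. If the Analysis section is followed as written, nothing in the output would show whether a non-significant result means a small change or too little information. At stake is what the study can say about Aim 2, and what it passes on to the larger studies that the Sample Size section has in mind.

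**Working it through.** The documents give no power, significance level or margin for these comparisons, so there is no stated figure to reproduce.

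**Inputs**
- n = 75 (Participants).
- Clinic rates for 2013 (Safety, before the stoppage rules): major bleed 1.88%, thromboembolism 0.22%, and "Serious bleed: 0.5% (95%CI 0.23-0.94%); range of 0-0.5"%. Sums, ignoring overlap: 1.88 + 0.22 = 2.10% a year; 2.10 + 0.50 = 2.60% a year.
- Baseline 12 months, on study up to 24 months: at most 75 and 150 patient-years.
- Assumed: two-sided 5%, the two periods independent within patient, Poisson events, no dropout.

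**Exact McNemar, 12 v 12 months, true doubling**
1. Chance of any event in a year: p = 1 − exp(−rate). At 2.6%, p₀ = 0.0257; doubled, p₁ = 0.0507.
2. Expected discordant patients: 75 × p₁(1 − p₀) = 3.7 with events on study only, and 75 × p₀(1 − p₁) = 1.8 with events at baseline only.
3. Five discordant patients, all one way, give p = 2 × 0.5⁵ = 0.0625. Six give 0.031. So at least six in one direction are needed.
4. Power summed over all discordant outcomes: 2.4% (base 2.1%) and 3.9% (base 2.6%). The asymptotic version gives 9.7% and 11.3%.

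**Paired t on annualised events, 12 v 24 months (the most favourable of the planned options examined)**
1. Per patient, d = (24-month count)/2 − (12-month count). With a doubling at 2.6%, mean d = 0.052 − 0.026 = 0.026.
2. Variance of d = 0.104/4 + 0.026 = 0.052. Standard error = √(0.052/75) = 0.0263. The expected change is about one standard error, against a critical value of 1.99.
3. Simulation (100,000 runs) gives 22% power at both base rates. With no change it rejects in about 8%, because the counts are sparse and skewed.

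**Effect of the 6-month event exclusion**

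The exclusion criteria rule out bleeding or thromboembolism that needed medical intervention in the previous 6 months, which is half of the baseline window. If a share f of events in those months is removed, the baseline rate is multiplied by (1 − f/2), and the apparent rate ratio with no true change is 1/(1 − f/2). The same paired t then rejects as follows (base 2.1% / 2.6%):

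| f | Apparent ratio, no change | Rejects, no change | Rejects, true doubling |
|---|---|---|---|
| 0 | 1.00 | 8 / 8% | 22 / 22% |
| 25% | 1.14 | 10 / 10% | 26 / 27% |
| 50% | 1.33 | 11 / 13% | 30 / 32% |
| 75% | 1.60 | 14 / 16% | 36 / 39% |
| 100% | 2.00 | 16 / 20% | 43 / 46% |

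f = 100% is an upper bound. If all major bleeds and thromboembolism but no serious bleeds are removed, the ratio is 2.6/(2.6 − 1.05) = 1.68.

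**What an interval would show (2.6% a year)**
- Expected events: 75 × 0.026 = 1.95 at baseline; 150 × 0.026 = 3.9 on study; 7.8 if doubled.
- 2 v 4 events: rate ratio 1.0, exact 95% CI 0.14 to 11.1.
- 2 v 8 events: rate ratio 2.0, CI 0.40 to 19.3, p = 0.51.
- On-study rate from 4 events: 4/150 = 2.67 per 100 patient-years (0.73 to 6.83). From 0 events the upper limit is 2.46.

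**TTR**

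Half-width of the 95% CI for mean change = 1.993 × SD/√75, which is 2.3, 3.5 or 4.6 points for an assumed SD of change of 10, 15 or 20. The documents give no SD.

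**The case against.** The strongest reply is that no false claim has been made. The hypotheses can be read as stated expectations, the Sample Size section calls this a feasibility study and leaves power to later work, and there is no equivalence claim to be wrong. That stands, and it is why no margin, power statement or larger sample is asked for. A reader might infer that the investigators will report non-significance as proof of safety; the documents do not say so. But the Analysis section offers no other route from the before/after data to the hypotheses.

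Safety is also not judged by these tests alone. There is a comparison with clinic rates, review by a data monitoring committee, and stoppage rules. So the point should not be read as saying that participants are unprotected. The clinic comparison does not fill the gap, though: it has no stated method, and the Background itself reports fewer events in stable patients, so it leans toward looking safe.

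The power figures use clinic-wide rates. If stable patients have lower rates, the base is too high and true power is lower still. The exclusion works the other way and pushes toward a false increase rather than false reassurance. Both are fair objections to treating 22% as a precise figure.

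Two further readings go too far. One is that the TTR comparison is also underpowered: at SDs of 10, 15 and 20, a paired t-test has 99, 81 and 57% power for a 5-point change. The other is that the utilisation analysis is wrong. Unequal windows would double raw counts with no true change, but annualising is compatible with the text and is what Aim 2 does for events. Only the scale is unstated.

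**Conclusion.** The concern holds for the Aim 2 before/after comparisons. For events, the planned tests are unreliable in both directions. A true doubling is detected in 2 to 4% (exact McNemar) to about 22% (annualised paired t, 12 v 24 months) of studies. With the exclusion allowed for, the latter becomes about 26 to 46%, and false rejection with no change rises to about 10 to 20%. A doubling is missed more often than not under every setting examined. This rests on n = 75 with full follow-up, the clinic's 2013 rates, two-sided 5% and independent periods.

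For TTR the point is one of logic only: an interval addresses a no-difference hypothesis and a p-value does not. For utilisation it is a clarification. The documents do not support a claim that the study is too small for its stated feasibility purpose. This should be fixed, and it is not an error in a stated calculation.

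**What to change.** In the Analysis section:
- Report baseline and on-study rates of major bleeding, serious bleeding and thromboembolism per 100 patient-years with exact Poisson 95% CIs, and a rate ratio or paired annualised difference with its CI.
- Report the paired TTR change with a 95% CI.
- State that a non-significant test will not be read as no difference.
- State that the 6-month event exclusion tilts the before/after comparison toward an increase, by an amount that depends on how many events it removes, and that selecting stable patients tilts the clinic comparison toward looking safe.

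As a clarification, in Measures item 2c, express utilisation per patient-year of actual time on study. Follow-up will differ between patients, with "no more data collected from the participant if they withdrawal their consent for the study or if death occurs".

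The cost is a few sentences and a little programming, with no new data or patients. The real price is a less favourable safety statement: a wide interval in place of a finding of no difference. The change does not make 75 patients enough for rare events. It shows the uncertainty, which is also what planning a larger study requires.

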A prospective cohort study is proposed to assess the feasibility, safety, and acceptability of extending the interval of INR follow-up to 12 weeks in stable warfarin patients. All participants consenting to study participation will have their INR follow-up interval extended according to the study protocol. If a participant's warfarin dose and INRs continue to be stable, the follow-up interval will be extended from 5-6 weeks, to 7-8 weeks, and then to 11-12 weeks. Participants will be surveyed to explore their opinions and satisfaction with the changes to their follow-up interval at various points in the study (baseline, 6 months, 12 months, 24 months). At the end of the study, a focus group will be held for a random subset of participants to obtain further information related to acceptability of this type of follow-up.

Additionally, we plan to assess anticoagulation clinic provider study staff's knowledge of the study protocol prior to the enrollment of participants for quality improvement and programmatic evaluation. At the end of the study, we also plan to hold a focus group for all anticoagulation clinic provider study staff to obtain further information related to the extended INR interval follow-up process.

Participants: We propose to enroll 75 eligible patients on warfarin from the William S. Middleton Memorial VA Hospital in Madison, WI and the Madison VA's associated community-based outreach clinics. Patients must also meet the following criteria to be invited to participate:

- 18 years of age or older
- requirement for indefinite warfarin therapy
- target INR of 2-3

- stable weekly warfarin dose for the past 6 months
 - not more than a single, one-time adjustment (boost/omission) in the past 6 months
 - planned interruption for a procedure or surgery with INR(s) out of range in the past 6 months would not exclude a patient
 - a patient of the Madison VA anticoagulation clinic for the previous 12 months
- Patients will not be eligible to participate in the study if they meet any of the following criteria:
- consistently drink ≥ 4 alcoholic beverages/day or a documented episode of alcohol binging in the past 6 months
 - diagnosis of cancer and on active chemotherapy/radiotherapy in the past 3 months
 - life expectancy of < 1 year
 - enrolled in other investigational drug protocols
 - only receiving anticoagulation care at the Madison VA for part of the year (e.g. snowbirds)
 - receiving visiting nurse services for INR monitoring

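### Aim 2 is framed in events per year, but none of the listed tests accounts for exposure time, and an exposure-adjusted comparison must also allow for the event-free half of the baseline year

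*Combined protocol and SAP*

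**What the plan says.** Specific Aims, Aim 2, hypothesises no difference in bleeding and thromboembolic events "from baseline (12 months prior to study enrollment) to events/year at 6, 12, and 24 months".

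The inferential plan in the Analysis section is one general sentence covering every outcome: "Differences from baseline and at study completion will be compared utilizing McNemar Test for categorical data and paired t-test", or the Wilcoxon signed-rank test, the last of these for ordinal data. It assigns no test to events and contains no person-time denominator, offset or rate ratio.

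Four other parts of the document bear on the comparison:

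- **Length of follow-up** (Safety): subject to the data monitoring committee's review, "the study will continue until patients have been enrolled in the study for 2 years".
- **Early end of follow-up** (Safety): there will be "no more data collected from the participant if they withdrawal their consent for the study or if death occurs".
- **Fatal events are outcomes** (Safety and Measures): the first criterion for a major bleed is "Fatal or symptomatic bleed into a critical area or organ".
- **Eligibility** (Participants): bleeding or thromboembolism that needed medical intervention in the previous 6 months is an exclusion. The target is 75 participants.

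Measures adds a comparison of participants' events with the clinic's event rate, but names no method.

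**The concern.** The hypothesis concerns a rate, so the analysis has to divide by time at risk. Taken as written, the listed tests leave two ways to handle events, and neither does this properly.

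- **Event yes or no, by McNemar.** At study completion this sets a 24-month window against a 12-month one. More participants will have had an event in the longer window even if risk has not changed.
- **Events per year as a continuous variable, by paired t-test.** Each participant's count is divided by that participant's own follow-up. An event that ends follow-up early is divided by a small number. A fatal event cannot occur at baseline, because everyone enrolled survived that year.

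Safety is one of three declared aims, and the Sample Size section says the results may inform the size and power of later studies. A distorted rate would carry forward into that planning.

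**Working it through.** **Inputs.** N = 75 (Participants). Clinic rates from the Safety section: major bleed 1.88%, serious bleed 0.5%, thromboembolism 0.22%. Their sum is 2.60%, read here as an annual rate. The comparator trial's composite rate is 4.8% per year (stoppage table). The plan states no alpha; two-sided 0.05 is assumed.

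**The plan's own figures.** It gives no power or sample-size figure for Aim 2. Its event rates reproduce with exact binomial intervals if the denominators are inferred as about 1805 (clinic of roughly 1800) and 250 (12/0.048):

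- 34/1805 = 1.88% (1.31 to 2.62)
- 4/250 = 1.6% (0.44 to 4.05)
- 12/250 = 4.8% (2.50 to 8.23)
- 50 × 8.2% = 4.1 expected events

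**Yes/no route, constant risk.** Expected participants with an event = 75 × (1 − exp(−rate × years)).

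| Rate per year | 12-month baseline | 24 months on study | False harm signal, exact / chi-square | Same, if both windows were 12 months |
|---|---|---|---|---|
| 2.6% | 1.92 | 3.80 | 3.9% / 11.0% | 0.2% / 2.0% |
| 4.8% | 3.51 | 6.87 | 10.8% / 16.6% | 0.75% / 2.3% |

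The signal probabilities come from enumerating the discordant pairs. The plan does not say which version of McNemar applies.

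**Individual-rate route.** Suppose one fatal event on day 30, no other events, and 74 participants followed for two years.

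- That participant's rate: 365.25/30 = 12.2 per year.
- Mean of individual rates: 12.175/75 = 0.162 per year.
- Pooled rate: 1/(74 × 2 + 30/365.25) = 1/148.08 = 0.0068 per year, about 24 times smaller.
- Paired t-test: with one non-zero difference x among n, the mean is x/n and the standard error is also x/n. So t = 1.00 and p = 0.32, whatever the day of the event.

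If everyone completes 24 months, the mean of individual rates equals the pooled rate and this problem disappears.

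**Pooled person-time.** With 2 events in 75 baseline patient-years and 4 in 150 on study, both rates are 2.67 per 100 patient-years and the ratio is 1.0. Given 6 events, the exact 95% interval for the study share is 0.223 to 0.957. Converting by share/(1 − share) × 75/150 gives a rate ratio interval of about 0.14 to 11.

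**Effect of the 6-month exclusion.** For events that needed medical intervention, only the first 6 of the 12 baseline months can contain one.

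- At-risk baseline time: 75 × 0.5 = 37.5 patient-years.
- Null share of events falling on study: 150/(150 + 37.5) = 0.80. Counting the full baseline year gives 150/225 = 0.667.
- If every outcome event meets the exclusion, about 0.97 participants are expected with a baseline event (75 × (1 − exp(−0.026 × 0.5))). Dividing about one event by 75 patient-years halves the baseline rate, so the rate ratio is about 2 with no change in risk.

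**The case against.** The strongest reply is that the Analysis sentence is generic and assigns no test to bleeding or thromboembolism. Events per year in Aim 2 could be read as a cohort rate, and nothing says that each person's count is divided by their own follow-up. This is fair: both routes are readings of the plan. But the sentence lists the only tests, and no other section supplies an exposure-adjusted one.

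A second reply is that this is a feasibility study with no power claim, and at about 2 against 4 events no method is informative. The low power is real. It is a reason to report an interpretable estimate with an interval, and does not justify comparing unequal windows.

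Four stronger readings may tempt a reader, and the documents do not support them:

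- **That early fatal events produce false significance.** They distort the estimate and leave the t-test at p = 0.32; the inflated variance can equally hide a signal. Nor is there a dependable average inflation. Assuming 20% of events end follow-up and 5% per year exit at random (neither is in the document), separate simulation runs gave means from 0.058 to 0.096 per year, because the expectation of 1/time diverges. The median was near 0.029, against 0.026 pooled.
- **That McNemar leans towards benefit at 6 months.** Aim 2 names 6 and 12 months, but the Analysis sentence tests only at study completion. At 12 months the windows would be equal.
- **That this is the only formal safety analysis.** Aim 2 also has a hypothesis on time in therapeutic range, and the Safety section has numerical stoppage rules and committee review.
- **That pooling person-time alone repairs the comparison.** The 6-month exclusion shows that it does not.

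**Conclusion.** The point holds in this limited form: the hypothesis is about a rate, and none of the listed tests accounts for exposure. The firmest consequence is the yes/no comparison at completion, where unequal windows roughly double the participants with an event at constant risk. The false harm probability is modest with the exact test and larger with the chi-square version or at the comparator trial's rate. The individual-rate distortion is conditional, arising only when death or consent withdrawal cuts follow-up short, and it affects the estimate rather than the p-value.

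These figures assume a constant event rate, clinic percentages that can be summed and read as annual, 75 enrolled, and full follow-up except where stated. How far the 6-month exclusion matters depends on how many outcome events needed medical intervention. A serious bleed that led only to additional testing may not have, so the two-fold baseline effect is the extreme case. The change should be made, but it does not threaten the feasibility aims.

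**What to change.** In the Analysis section, for bleeding and thromboembolic events only:

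1. Replace the listed tests with total events over total patient-years in each period, ending each person's time at death or consent withdrawal.
2. Report a rate ratio with an exact conditional 95% confidence interval, or use a Poisson model with a log person-time offset, clustered by participant.
3. For events needing medical intervention, restrict the baseline to the months in which one could have occurred (about 37.5 patient-years, null share about 0.80 with full follow-up), or show this as a sensitivity analysis. Do not use 0.667 for these events.
4. State that fatal events cannot occur in the baseline year, and that a non-significant result does not establish absence of a difference.

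Keep the paired t-test and Wilcoxon for time in therapeutic range and survey scores.

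The cost is one paragraph, plus confirmation that event and exit dates are captured. The list of data from the medical record asks for dates with INRs but lists bleeding and clotting events without them. The interval will be wide: about 0.14 to 11 at 2 versus 4 events, before the baseline restriction removes information.
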